The data collected in this study will be used to prepare a NIH RO1 application, which will launch my independent program of research. Using NMES to improve exercise use in patients with HF is of specific interest to the NIH due to all the potential improvements previously discussed. There is a great potential for extramural funding for development of non-pharmacologic interventions that maintain/improve independence, increase quality of life, decrease hospitalizations, and improve patient outcomes. This study will add to the science by determining if NMES can be used as a stepping stone for enrollment into formalized exercise rehabilitation program, or as an approach for those who are unable to exercise.

Section 3: Inclusion and Exclusion Criteria

Inclusion criteria

Adult patients with a recent hospitalization or clinic visit for heart failure, (ICD-9 428; ICD-10 I50) and one of the following: BNP >400 OR NT-proBNP>900 (If renal dysfunction >1200) OR Echo showing myocardial remodeling, dilation, hypertrophy, or dysfunction will be included in this study. In addition patients must live at home, and not regularly exercise (10 minutes or more a day of exercise most days of the week for the past week).²⁵ Sedentary patients are the focus of this intervention because they would most likely see significant improvement with the intervention.

Exclusion criteria

Patients, who have undertaken cardiac rehab within the 12 months prior to enrollment, have a cognitive or other impairment which prevents accurate application of intervention or inability to provide informed consent, End Stage Renal Disease or receiving mechanical ventilation, receiving non-approved FDA-investigational agents or devices, has received a heart transplant, a destination Ventricular Assist Device (LVAD), pacemaker, or implantable cardiac device, previously used NMES (Neuromuscular electrical stimulation) or TENS (Transcutaneous electrical nerve stimulation) or Uncontrolled arrhythmia's or 3 degree AV heart block, are unable to correctly apply and operate the device even after instruction (as determined by the Research Assistant), those with wounds over area of proper placement of electrodes, or those who are unable to speak and write English. Women who are pregnant or planning to become pregnant.

Children will not be included in this study. Although HF can occur in all ages, it is primarily a disorder of the elderly. In addition the causes of HF in children is very different than adults.

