Section 4: Enrollment and Randomization

Patients who meet eligibility criteria will be referred to the investigator or the research assistant by cardiology, heart failure, or emergency room providers during their routine evaluation of patients eligible for participation in other heart failure research studies through the medical record system. In addition, a clinical research systems

request has been made to allow for notification to the PI the identification all heart failure patients admitted to the hospital so the PI or RA can screen for eligibility. In addition, [name] will release names and contact information for previous participants in her HF study to the PI if the participant has previously indicated they would like to be contacted for future research studies for screening to determine eligibility to participate in this study. The patient will then be contacted by a BISTRO team member for a full explanation of the study and determine interest in participating. If they are interested and are also willing to participate in the FIT Core study (IRB #170755085), an appointment for follow up discussion and possible consenting for both studies) will then be set up for the following week or two. At which time they will come to the school of nursing for final consideration, potential consenting, begin data collection.

In order to ensure that the two groups are comparable between treatment and sham interventions, the participants will be randomized according to gender. Randomization via minimization will be used in order to avoid an unbalanced number of women in the two comparison groups due to chance.²⁶ A file of the computer-generated random assignments will be kept by the research assistant so the PI/data collector remains blinded in a protected Box Health account.

Section 5: Study Procedures

Intervention and Sham/Wait List Control Conditions

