The PI will collect all baseline data before the participant is randomized to the intervention or sham/wait list control group. In order to ensure rigor, patients and PI are blinded to study assignment. The intervention/sham will be set-up by the RA and will be collected after the PI leaves the department so those collecting data will not know which group the participant has been/will be participating in. The RA who is trained in both NMES and Sham intervention will then look at the randomization schedule, and set up and train the participants on equipment use after the data has been collected.²⁷ Once trained, participants will be contacted via phone weekly by the RA who initially trained them (in order to maintain blinding) to determine if participants are following protocol and placement as taught, if the participant is tolerating the intervention, skin condition under the electrodes, and if there are any questions or problems with the machine. The RA applying the intervention will not have any part in the data collection of the rest of the measurements (other than adherence, tolerance and problems with equipment).

The Empi Continuum electrotherapy system made by Empi, Inc. (Clear Lake, South Dakota) is chosen for NMES in this study because it is already available to the PI, it has both the intervention and sham settings, and is able to track adherence (total number of sessions, total session time, average session time, average intensity). Each machine will be calibrated before use for each participant and also checked with each return visit. The output of the stimulator will be checked with an oscilloscope to ensure consistency between the current reading on the stimulator and the actual current output every time the participant returns. NMES will be set up with the machine on simultaneous large muscle atrophy setting with 500 ohm with peak of 50 volts, the “self-adhesive electrodes positioned on the thighs approximately 5 cm below the inguinal fold and 3 cm above the upper patella border” as described by Gobbo.²⁸ When applying the stimulation, the intensity will be gradually increased from an intermittent tingling until a

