gentle pumping sensation is felt. Participants will direct the amount of stimulation acceptable on both thighs to improve acceptance of the modality.^{10,24,29-31} To assist better tolerance large electrodes (2x4) will be used and participants will also be instructed to be in a seated position with chair close to the wall so that their leg is 90-degree angle and then push against the wall to decrease any uncomfortable feeling during the contraction. For the Sham group, electrodes will follow the same landmarks, but the stimulation will only increase to an intermittent tingling sensation with the machine setting on TENS instead of NMES which is not enough to make noticeable changes in muscle mass or circulation.³² Participants in both groups will be given written instructions and contact information of the person (RA) to contact should there be any problems or concerns with the intervention. All participants will do a return demonstration to assure proper knowledge has been gained. Adherence to the study protocol will be determined by the amount of time the EMPI machine records that it was used, the intensities utilized along with verbal verification during the weekly phone calls.

NMES Protocol Summary

- 5 sessions per week for 6 weeks done independently at home, with 15 minutes per session (15 stimulations per day/session, 15 seconds stimulation on, 15 seconds recovery time) to both legs.
- Intervention group only: We expect the participant to develop tolerance to the treatment and thus increase the intensity of the NMES over time.
- At the end of the trial, the participants will return to have all measures repeated. Sham group will then be offered the active treatment. In previous HF studies (non-NMES) done by the mentor of this grant, no participants have accepted the offer of the intervention after completion of the sham/control so this number is expected to be very small.
- Participants will be encouraged to begin a formalized exercise plan such as Silver Sneakers, a home based cardiac rehabilitation or institutional cardiac rehabilitation program.
- Finally, 3 months after the intervention/sham was completed participants will return one final time to have all measures repeated to allow for evaluation of activity levels following completion of the intervention.

Retention

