- 3) [name], RN, FAAN, Independent reviewer, School of Nursing Associate Dean for Research, Distinguished Professor, will perform an independent review of the expected/unexpected adverse event data to assure non-bias by the PI on a monthly basis.

Minimizing research-associated risk.

- Protocols for teaching patients how to safely apply the electrodes and monitor their skin will be verbalized with the patient. Following the teaching the patient will teach back what was learned. If not complete or correct, additional information will be given with the patient again verbalizing all key points. If the patient is unable to complete this task, they will be excluded from the study. We will provide written handouts with directions and pictures of proper placement of electrodes. The RA will call the patients weekly while they are using the EMPI machine to determine safety and potential skin irritation or muscle soreness.
- For patients who have scores on the PHQ-8 suggestive of high depressive symptoms (scores > 10) [name] will follow-up with patients' individual physicians after alerting the patient.
- Adherence to the safety protocols will be reviewed at weekly team meetings and at monthly Co-Investigator meetings. In addition, [name] will provide continuous, close monitoring of protocol adherence and referral of patients if needed.

[name] will be responsible for reporting unexpected adverse events and unanticipated problems as required by the IU IRB. The IU IRB will be notified in writing of adverse events within 5 business days of identification of events. During each visit, the PI or RA will question the patient about adverse events using an open question, taking care not to influence the patient's answers, e.g. "Have you had any unusual symptoms or medical problems since the last visit?" It is expected that many HF patients will have events that are commonplace due to their HF and associated comorbidities.

Determining if an Adverse Event needs to be reported to the IRB

1. Is the occurrence **unexpected** during the course of the study?
 - a. We expect skin irritation and minor muscle soreness, complications that occur as a result of protocol-mandated use of the EMPI machine, these events will not be reported.
2. Is the occurrence related (or possibly related) to the study?
 - a. Not including the expected events, if yes and unexpected, then the event will be reported to the IRB.
3. Does the event put participants at greater risk of harm?

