The research associate will review all data collected for completeness and readability, correcting any errors prior to data analysis. We will collect "reason for drop out" if a participant stops the study. We will continue to try to schedule subsequent data collection interviews even if the participant is not able to complete a previous one. During each data collection session, team members will work with participants to encourage response to all items and will review data to ensure all data points are completed unless the participant prefers not to answer. Nonetheless, missing data will occur and this will be acknowledged in the analysis.⁷⁶ We will conduct initial analyses using the maximum likelihood approach, as it emphasizes the use of all available data. The use of random effects modeling techniques, in particular repeated measures mixed modeling, allows for missing data by adjusting the estimation process to account for bias resulting from data missing at random. Baseline data from those with and without missing data will be compared to determine whether there are systematic differences, using demographic and personal variables. If the data are not amenable to the maximum likelihood method random effects analysis, multiple imputation will be used as an alternative procedure for handling missing data. Multiple imputation produces results similar to maximum likelihood when used under identical conditions. We will use multiple imputation in the sensitivity analyses; this will allow for the comparison of study results under a variety of assumptions to assess the robustness of the findings.

Statistical Analysis

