2. Obtain the ActivPAL. Orient it so that the body on the ActivPAL is standing up. (See picture above.) You will notice the rounded side is up, and the square side is down. Lights face away from your skin.
3. Cover the ActivPAL with the waterproof covering and roll the end to the side away from you.
4. Sit down on a chair when attaching the monitor so that it will be easier to find the best place for attachment. You want to place it on the top 1/3rd of the length between your groin and your knee in the midline width of your thigh as shown in the picture below.

5. Apply the Skin-PREP wipe to the area of skin where the ActivPAL will be. This will protect your skin from the adhesives in the tape and allow the tape to perform better.
6. Place the covered ActivPAL in the correct orientation on the upper thigh. See picture above. The ActivPAL should be worn on your non-dominant side.
7. Use a large piece of Tegaderm tape to completely cover the ActivPAL. Ensure that this adheres directly to the skin.

Removing the ActivPAL:

1. Carefully peel the Tegaderm away from the skin by lifting up a single corner of the material and gently pulling away from your skin, but level to the bandage.
2. Remove the ActivPAL, encased in its waterproof covering, from the skin.
3. Carefully wash and dry the skin where the ActivPAL was applied with mild soap. If skin irritation has occurred, please contact research assistant.
4. Place the ActivPAL in the bubble mailer we gave to you and place it in any US mail box for return to us.
5. ActivPAL needs to be received by us before we can issue your study participation check.

If you have any questions about the ActivPAL or the study at any time please call the research assistant.

Thank you for participating in our study!

Section 12B SOP for EMPI

EMPI Standard Operating Procedure for setting up TENS

Machine Set up: do this before you see the participant. Please note, you may not need to make adjustments to the machine due to previous programming, so if the correct option is chosen move on to the next item.

1. Turn on machine
2. Press “Home” button
3. Press the TENS button (bottom Left)
4. Press the lower left bottom button until “Custom”, then press OK
5. Change “Time” to 15 MIN, Use the right buttons to raise or lower to 15 MIN, then press bottom left button to progress to “Rate”.
6. Leave “Rate” at 100Hz , then press the bottom left button to progress “Cycle”

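### Device competence is tested after allocation by a research assistant who knows the arm, and the plan does not say that participants excluded for failing are still measured or analysed in their allocated group

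*Combined protocol and SAP*

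**What the plan says.** On timing, Section 5 (Intervention and Sham/Wait List Control Conditions) states: "The PI will collect all baseline data before the participant is randomized". The RA "will then look at the randomization schedule, and set up and train the participants on equipment use after the data has been collected". Later in the same section: "All participants will do a return demonstration to assure proper knowledge has been gained".

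On who knows the arm, Section 4 states: "A file of the computer-generated random assignments will be kept by the research assistant". The purpose given is to keep the PI, who collects the data, blinded. The set-up procedures in Section 12B are separate for TENS (sham) and NMES, and each begins: "Machine Set up: do this before you see the participant".

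On the consequence of failure, there are two rules. Section 3 excludes people who "are unable to correctly apply and operate the device even after instruction (as determined by the Research Assistant". Section 6 (Minimizing research-associated risk) asks the patient to teach back electrode application and skin monitoring, gives further information if the answer is incomplete or wrong, and then says "If the patient is unable to complete this task, they will be excluded from the study". It does not name who judges this.

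On follow-up and analysis, Section 8 (Missing Data) says "We will conduct initial analyses using the maximum likelihood approach, as it emphasizes the use of all available data". It also plans to keep scheduling people who miss a session, to record reasons for drop-out, and to compare baseline data between those with and without missing data. Section 7 covers voluntary withdrawal only. Section 8 (Power Considerations) counts at least 27 completers per group. No analysis set is defined.

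**The concern.** A competence check is harmless before allocation, where failure is a screening exclusion. After allocation it removes a randomised participant, and here one of the two rules leaves the decision to someone who knows the arm. The comparison then rests partly on who was judged able to use the device.

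What is at stake depends on two things the plan leaves open: whether removed participants are still measured, and whether they are counted in their allocated group. If only a baseline record remains, it protects the analysis when failure depends on baseline status. It does not protect against failure linked to later decline. Nor does it help Aim 4, because enrolment in an exercise programme has no baseline value.

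**Working it through.** **1. Order of events.** Section 5 gives: baseline data; randomisation; RA reads the schedule; RA sets up and trains; return demonstration. Section 12B has the arm-specific unit programmed before the RA meets the participant. The Section 3 criterion applies only after instruction has been given, and the only device instruction described comes after the look-up. On the text as written, both competence rules therefore operate after allocation.

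**2. Does any text cover those who fail?** Section 7 concerns people who choose to leave. The rescheduling sentence in Section 8 concerns people unable to complete an earlier session. Neither describes someone removed by the study. The baseline comparison in Section 8 does imply that records of people without outcomes are kept.

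**3. Which correlation fits the plan?** Power Considerations calls the within-person correlation modest and gives no number. I recovered it from the stated powers, with N = 54 and 3 time points:
- Group: λ = f²·54·3/(1 + 2ρ), df 1 and 52.
- Time by Group: λ = f²·54·3/(1 − ρ), df 2 and 104.

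At ρ = 0.32:
- Group, f = 0.4: λ = 25.92/1.64 = 15.8, power 97.4% (stated 97%).
- Group, f = 0.25: λ = 10.125/1.64 = 6.17, power 68.4% (stated 69%).
- Time by Group, f = 0.25: λ = 10.125/0.68 = 14.9, power 93.6% (stated 95%).

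All three agree within 2 points for ρ between 0.305 and 0.345. I use r = 0.3 below.

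**4. Failure that depends on baseline, baseline kept.** Baseline is one of the modelled time points, so this is missingness explained by observed data. Simulation of the likelihood analysis gave a bias in change of 0.000 to −0.001 SD, which is effectively nil.

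**5. Failure linked to later decline (illustration).** Assumptions, none supported by the documents:
- no true effect, and outcome SD 1;
- k failures, all in one arm, beside 27 completers;
- a failure score correlated c = 0.6 with decline that is independent of baseline.

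Formulas:
- share lost: q = k/(27 + k);
- shift in the driver: m = c·φ(z_q)/(1 − q);
- shift in change: d = m·√[(1 − r)(1 + 2r)/2] = 0.748·m at r = 0.3;
- noncentrality of the Time by Group test: (27/2)(2/3)d²/(1 − r), df 2 and 104.

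| k | q | φ(z_q) | m | d (SD) | Noncentrality | Rejection rate |
|---|---|---|---|---|---|---|
| 1 | 0.036 | 0.079 | 0.049 | 0.037 | 0.017 | 5.1% |
| 3 | 0.100 | 0.175 | 0.117 | 0.088 | 0.099 | 5.7% |
| 5 | 0.156 | 0.240 | 0.170 | 0.127 | 0.209 | 6.6% |

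Halving c to 0.3 halves d and quarters the noncentrality; at k = 5 the rate is then 5.4%. Keeping the baseline record does not remove this shift. Failures spread equally over both arms for the same reasons would produce none.

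**6. Aim 4.** With k people unmeasured, the allocated-arm enrolment proportion is undetermined over k/(27 + k): 3.6, 10.0 or 15.6 percentage points. This bound applies to any missing participant and is not specific to this rule.

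**The case against.** The strongest reply is that Section 3 lists the device criterion under eligibility, so screening was probably intended. That may be so, but no instruction or check before allocation is described; if screening was meant, the order of the text needs to change.

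Second, failure should be rare. Section 3 separately excludes impairments that prevent accurate application, Section 6 gives further teaching before exclusion, and written handouts with pictures are supplied. This stands. Five failures in one arm is an extreme case.

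Third, a reader might infer that the NMES arm would lose more people, because the Section 12B procedures ask NMES users to reach a contraction and sham users to stay below one. The documents do not support that. The Section 6 teach-back is the same in both arms, and no text makes failure to reach an intensity a ground for exclusion. Differential exclusion is possible through the word 'operate' in Section 3, but it is not shown.

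Fourth, a reader might infer that excluded participants' baseline records are discarded. At r = 0.3, c = 0.6 and k = 5, that would shift change by −0.7 × 0.170 = −0.119 SD if failure followed baseline. Section 8 points the other way: it uses all the data at hand and compares baseline data of those with and without missing values. What it leaves unsaid is whether removed people are measured again and counted as allocated.

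**Conclusion.** The point holds as a minor one. The written sequence permits exclusion after randomisation, with an unblinded judge under Section 3, and nothing secures outcome measurement or as-allocated analysis for those excluded.

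Size and direction are unknown and may be nil. Where failure follows baseline and records are kept, the bias is about zero. Where failure is tied to later decline and falls wholly in one arm, the illustration gives false-positive rates of 5.1% to 6.6%. That range rests on the assumed number of failures, their one-sidedness, c = 0.6 and r = 0.3; only the last has indirect support, from the plan's own power figures. Larger error rates would need a within-person correlation well above the modest one the plan assumes. The case for acting is that the remedy is cheap, not that harm has been shown.

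**What to change.** 1. In Section 5 and the Section 12B set-up procedures, do the teach-back of the steps common to both arms (electrode placement, skin care, on/off and buttons) before the RA opens the schedule. Because the RA holds the assignment file, record the result in REDCap first. Failure at that stage is then a screening exclusion. Programming of the unit moves to after this step.

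2. Arm-specific intensity setting still follows allocation, so some failures could still occur afterwards. Add to Section 6: *An allocated participant who then fails the device task is still invited to all outcome measurements, where willing, and the baseline record is kept; numbers and reasons are reported by arm.* Add to Section 8 (Statistical Analysis): *All randomised participants are analysed in their allocated group, including those with baseline data only.*

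The rule on who may use the device is left to the sponsor.

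The cost is two added sentences, a change of order, a few minutes of training for people who then screen out, a short wait while the unit is programmed, and a few extra outcome visits. Allocated non-users also dilute that arm's effect by their share if they gain nothing: about 4% for 1 of 28, and 16% in the extreme case of 5 of 32.
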